Aim 2. Test the hypothesized electrophysiological mechanism and rule out a placebo effect as cause for the symptomatic benefit, using randomized allocation of rhythmic stimulation to a control condition, namely random (not rhythmic) stimulation.

Aim 3. Gather additional preliminary information for a future clinical efficacy trial and NIH grant application. This information will include (a) the duration of effect after the end of stimulation, which is crucial information for designing chronic treatment, and (b) preliminary information on individual

characteristics that predict improvement with simulation, e.g. demographics, tic severity, premonitory urges, sensory hypersensitivity, ADHD, tic suppression ability, and tic phenomenology.

Completion of these Aims will give a clear go/no-go signal for a future clinical trial of chronic MNS delivered by a portable, wristwatch-style device.

STUDY DESIGN

Overall study timeline

The study will complete enrollment within 11 months and complete all human subjects procedures within 1 year.

Overview of each subject's participation

First we screen potential participants to ensure they meet criteria for study enrollment, and characterize their symptoms and other demographic and clinical features. They then participate in 2 stimulation sessions, at least a week apart, which are identical except that one session uses rhythmic and one uses arrhythmic MNS with the same number of total pulses per minute. Session order is randomized and participants are blinded to order. (Biological carryover effects are very unlikely.) Tics before, during and after stimulation epochs are video recorded for later analysis blind to time, stimulation (on *vs.* off), and stimulation type (rhythmic *vs.* arrhythmic).

Recruitment

Sources may include clinical referrals, online advertising, and word of mouth. We will also involve the local chapter of the Tourette Association of America, which is a key part of our TAA Center of Excellence

Prior to first visit

1. REDCap presents an informed consent document to parents of potential child participants explaining the study, risks and benefits of participation and that participation is voluntary. The ICD will be provided online prior to the in-person visit. Adult participants will provide their own informed consent. For child participants, consent from one parent or guardian is sufficient, as the study is minimal risk. Children must assent to participate.

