2. Attach electrodes (so they're visible in the baseline video for optimal blinding).
3. Check resistance through electrodes. If $< 100 \Omega$, look for a short and correct it. If resistance remains out of range, do not proceed without specific approval from PI. Record resistance.
4. Optional but recommended bathroom stop
5. Procedures below are performed in a quiet room with only participant and study staff present but not conversing
6. All videos are recorded from the elbows up for later blinded ratings of tics
7. 5-min video-recorded baseline session, also rated live at the first visit to record baseline tic

frequency

8. At this point, the PI or designate will review the inclusion and exclusion criteria (including mean baseline tic frequency $\geq 1/\text{min.}$) and document eligibility for the study before additional procedures
9. Determine stimulation threshold for a train of 8 pulses (12 Hz, pulse width 200 μs), starting at 1mA and increasing until a twitch of the thumb is seen, to a maximum of 20mA (expected range 2-15 mA, *personal communication, [name] to [name]*). Some subjects may wish to withdraw at this point if suprathreshold stimulation is too uncomfortable, but in the Nottingham report, participants age 15 and up found the stimulation tolerable. Since electrode placement can change slightly between visits, on the second visit the threshold is verified and adjusted as needed. We record the threshold at each visit.
10. Resume video recording
11. Synchronize clocks for video, urge rating software, and stimulation
12. MNS stimulation on or off blocks as follows, without planned breaks (total 29-44 min.)
 - a. Two 1-min. blocks of MNS on and two 1-min. sessions off, the order of these 4 sessions randomized (*this design matches the Nottingham study*)
 - b. 5-min. block MNS off
 - c. 5-min. block MNS on
 - d. 5-min. block MNS off
 - e. 5-min. block MNS on
 - f. 5-minute stimulation **off** blocks until tics return to baseline frequency (min. 1 block, max. 4 blocks)
13. Stop video recording
14. CGI-I (Clinical Global Impression of Improvement) rating for tics by participant and investigator
15. Debrief
 - a. ratings of tic improvement and discomfort using the CGI Efficacy Index
 - b. ask for comments on benefit, tolerability, side effects
 - c. participant and staff guess whether this was active or control stimulation day (*to test adequacy of blinding*)
 - d. ask if they think they would use a portable stimulator

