[Time Frame: 5-25 minutes after the end of stimulation at each study visit up to 1 month]

12. Interest in a portable stimulator

Participants answer the question, "If you had a portable device (about the size of a deck of cards) that delivered stimulation in your daily life like you received either today or at your previous visit, would you expect to use it?"

[Time Frame: Once at the end of the second study visit]

Data analysis

Data storage, sharing and management. Phenotypic data will be collected and stored on REDCap (redcap.wustl.edu). This data will not contain PHI and will be shared on the [Open Science Framework](#). Video recordings will be shared only with explicit optional informed consent.

Overall statistical approach. To prevent "HARKing" (hypothesizing after results are known) [20], we have **registered our hypotheses** and analysis strategy on [OSF.io](#) prior to initiating enrollment. For this pilot study, all statistical tests will be reported independently. Aim 1 and Aim 2 test a small number of hypotheses, and Aim 3 results, which are primarily hypothesis-generating, will be presented with a warning about multiplicity of tests.

Aim 1 (replicating the Nottingham results). The analysis will replicate that of Study 3 in the **Current Biology** report [6], with blinded ratings of tic frequency and severity based on the last 40 s of each 60-s MNS on or off block. A one-tailed t test will compare mean tic frequency in on *vs.* off 1-minute stimulation epochs on the rhythmic MNS day. The analysis will be repeated for tic severity.

Aim 2 (testing whether benefit from rhythmic stimulation exceeds that from the active control, arrhythmic stimulation). Change in tic frequency and severity from baseline are compared between MNS-on epochs on rhythmic *vs.* arrhythmic days. Subjects who do not complete both stimulation visits will not be included in this analysis. A repeated measures ANOVA will be used to compare effects of visit, order (rhythmic day first or second) and stimulation (on *vs.* off) on tic frequency and

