severity. The hypothesized change is a significant interaction of visit, order and stimulation factors ($p \leq .05$), showing greater improvement (off to on) with rhythmic *vs.* arrhythmic stimulation. The primary analysis will focus on the first six 5-minute blocks (*i.e.*, the ones that all participants complete). A secondary analysis examines the last 40 s of the four 1-minute blocks in the same way. Paired t tests will compare CGI-I ratings between stimulation conditions (rhythmic *vs.* arrhythmic).

Aim 2 interpretation: We chose arrhythmic stimulation as the control condition (“placebo”) because it did not increase stimulation-frequency EEG power in the sensorimotor cortex. However, we note that arrhythmic stimulation may itself possibly confer active benefit, which may produce a non-significant result for Aim 2. In that case a different control condition may be required for subsequent study, such as sub-motor-threshold stimulation current or a wait list condition. Additionally, this pilot study will not address the specificity of the stimulation site—as stimulation of another peripheral nerve may prove equally effective—nor the specificity of the 10-12 Hz stimulation frequency. Finally, other modifications may provide greater benefit; *e.g.* bilateral stimulation may be more effective than unilateral. All of these possibilities are reasonable goals of future study, but this pilot study focuses on the methods used in the published work.

Aim 3. The duration of benefit analysis will use a repeated measures ANOVA for tic scores from each 1-minute segment after the end of stimulation. A secondary approach may be to fit the tic scores from each participant after the end of each stimulation block to an exponential decay model. The analysis of individual characteristics that predict improvement with simulation will use a 2-tailed t test or correlation, as appropriate, for each measured demographic and clinical feature. These will include age, sex, baseline YGTSS, baseline OCD severity rating, baseline ADHD severity rating, history of complex tic(s), history of phonic tic(s), and motor and phonic tic frequency and severity at baseline (blinded ratings of the 5-minute block before stimulation on the first study visit). Other outcome variables, such as discomfort, adequacy of blinding, and interest in a portable stimulator, will be summarized descriptively.

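### Outcome 12 asks about a portable stimulator once, pooling both days, so the answer cannot be assigned to rhythmic or arrhythmic stimulation, and its timing conflicts with step 15d

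*Combined protocol and SAP*

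**What the plan says.** All references are to the combined protocol and SAP.

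- **Design** (Overview of each subject's participation): there are two sessions, of which "one session uses rhythmic and one uses arrhythmic MNS with the same number of total pulses per minute". On allocation: "Session order is randomized and participants are blinded to order".
- **Outcome definition** (Secondary Outcome Measure 12): participants are asked whether, given a portable device "that delivered stimulation in your daily life like you received either today or at your previous visit, would you expect to use it". The time frame is "Once at the end of the second study visit".
- **Procedure** (Stimulation protocol, step 15d, within the debrief): staff are to "ask if they think they would use a portable stimulator". The schedules for the first and the second visit both send the participant through this stimulation protocol.
- **Analysis** (Data analysis, Aim 3): "Other outcome variables, such as discomfort, adequacy of blinding, and interest in a portable stimulator, will be summarized descriptively".
- **Purpose** (Objectives): "Completion of these Aims will give a clear go/no-go signal for a future clinical trial of chronic MNS", to be delivered by a portable device.

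**The concern.** Two things look wrong. First, the item joins the two days with an either/or and takes one answer. The result is a single proportion that does not say which stimulation pattern participants had in mind. Someone reading the results could take it as interest in the active treatment, although the Aim 2 interpretation text itself allows that the arrhythmic control may give some benefit, so a yes prompted by the control day is plausible.

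Second, the outcome definition and the procedure disagree on when the question is put. Staff working from the debrief list would ask it twice. Staff working from the outcome definition would ask it once.

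What is at stake is whether a minor result can be interpreted, in a pilot meant to inform a later trial of a portable device. No primary analysis is affected.

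**Working it through.** The plan states no rate, sample size or power for Outcome 12, so there is no figure to reproduce. The check is a reading of the sections together, plus a short calculation of what one pooled answer can identify.

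**1. State of the participant when asked.** Everyone asked at the end of visit 2 has had both patterns. Splitting the answers by randomized order therefore does not separate the conditions: both order groups have had both, and the answer is not tied to a visit.

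**2. What a pooled yes identifies.** Let R be the share who would use rhythmic stimulation and A the share who would use arrhythmic stimulation. Read yes as willing to use at least one of the two. Then

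P(yes) = R + A - P(both), so max(R, A) ≤ P(yes) ≤ min(1, R + A).

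Given only P(yes), the difference R - A can lie anywhere from -P(yes) (every yes concerns arrhythmic only) to +P(yes) (every yes concerns rhythmic only). With the planned 32 completers and assumed counts:

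| Yes answers (assumed) | P(yes) | Possible R - A, points |
|---|---|---|
| 8 | 8/32 = 25% | -25 to +25 |
| 16 | 16/32 = 50% | -50 to +50 |
| 24 | 24/32 = 75% | -75 to +75 |

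Not even the sign of the difference is fixed.

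**3. Size of any overstatement.** This needs R and A, which the documents do not give. Purely for scale, take R = 50% and A = 40%. P(yes) is then 50% if the two groups overlap fully, 1 - 0.5 × 0.6 = 70% if they are independent, and 50% + 40% = 90% if nobody would use both. The excess over R is 0, 20 or 40 points. The range includes zero and depends wholly on assumed inputs.

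**4. Timing.** Steps of the stimulation protocol that apply to one visit only say so: live rating of the baseline is tied to the first visit, re-checking of the threshold to the second, and step 16 to the first. Step 15d carries no such limit. Read literally, it applies at both visits, which contradicts Outcome 12's single asking.

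**5. What is collected by day elsewhere.** Outcomes 6 (participant CGI-I), 9 (therapeutic effect) and 10 (discomfort) all have an each-visit time frame and can be split by condition. The upper anchors of Outcome 10 come close to asking whether the participant would keep the device on. Aim 2 also plans paired t tests of CGI-I between conditions.

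**6. Who is not asked.** Under Outcome 12, people who finish visit 1 and do not return give no answer. Their number cannot be derived, because the 27% allowance (44 enrolled to reach 32) combines screen failures with dropouts. People who withdraw at threshold setting (step 9) leave before any debrief and would be missed at either timing.

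**7. What a per-visit item could show.** With 32 pairs and assumed discordant shares of 30% vs 5%, 30% vs 10% and 40% vs 10%, exact McNemar power (two-sided 0.05) is about 61%, 33% and 62%. A per-visit version would also be descriptive.

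**The case against.** The strongest reply is that nothing planned fails. The item is the last of twelve outcomes, is only to be described, and has no planned contrast by condition. Asking blinded participants once, after both experiences, is a reasonable way to gauge general interest in a wearable, and the plan never claims that the item isolates the active treatment. Step 15d may be checklist shorthand for the fully worded question, which makes sense only at visit 2. If step 15d is in fact asked and recorded at both visits, the study will hold answers by day anyway.

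Most of this stands, and it rules out several stronger readings that a reader might infer:

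- *That the go/no-go signal is compromised.* The plan ties that signal to completing the Aims. Portable-device interest is not among the items the Aims list, though the Aim 3 analysis paragraph covers it, and no decision rule uses it.
- *That acceptability cannot be compared between patterns.* Outcomes 6, 9 and 10 largely allow this.
- *That interest in active treatment is overstated by a known amount.* The rates are not in the documents. The upper bound requires that nobody would use both patterns, although the sessions differ only in rhythm. A participant might also take the question to mean stimulation of this general kind, in which case the bound in step 2 does not apply.
- *That people put off by stimulation are lost and a per-visit question recovers them.* It recovers only those who reach the first debrief, and they have already rated discomfort there.

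Two things survive. The pooled answer still does not say what it is interest in, and the two sections still disagree on timing. A general-interest rationale is possible, but it is not stated.

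**Conclusion.** The point holds as a minor one. Outcome 12 as defined cannot be attributed to the rhythmic or the arrhythmic day, and its time frame does not match step 15d. The first conclusion follows from the wording and the crossover design and needs no assumed rate. The second assumes that step 15d means what it literally says.

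The impact is small. How far the pooled figure might exceed interest in rhythmic stimulation cannot be derived from the documents; the figures in the working are illustrations that depend on assumed counts or rates and on reading yes as at least one of the two. The finding does not touch the primary outcomes.

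**What to change.** Reconcile Outcome 12 with step 15d as follows:

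- At the end of each visit, ask whether the participant would use a portable device delivering the stimulation received that day.
- Tabulate the answers descriptively by condition (rhythmic, arrhythmic), with the paired difference for those who answered at both visits. Include in the by-condition table participants who completed only the first visit's debrief.
- Change the time frame of Outcome 12 to each study visit.
- Keep the pooled question at visit 2 as an optional extra.

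The cost is one extra short item and an edit to the outcome definition and time frame, with no added visit or procedure. Asking about that day's session does not reveal the condition. The comparison stays descriptive at N = 32 and should be labelled so.

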From these data, a sample size of 32 will have 81% power to find a statistically significant result for Aim 1 (two tails) assuming the population mean response is the 30% reported by our colleagues in Nottingham. This sample size provides 75% power to detect clinically meaningful (-25%) improvement (one tailed).

Estimating screen failures and dropouts at a total rate of 27%, we will plan to enroll up to 44 participants to arrive at 32 who complete the entire study.

INCLUSION CRITERIA

Inclusion criteria for all subjects:

- Age 15-64 inclusive at initial screening visit
- Informed consent by adult subject; assent by child and informed consent by guardian
- Current DSM-5 Tourette's Disorder or Persistent (Chronic) Tic Disorder
- At least 1 tic per minute (average) during the first 5-min. baseline video session on the first visit (as scored during the session by the investigator)

EXCLUSION CRITERIA

Exclusion criteria for all subjects:

- Unable to complete study procedures for any reason
- Has an implanted device that could be affected by electrical current
- Pregnancy known to participant or (for children) to the parent
- Known or suspected primary genetic syndrome (e.g. Down syndrome, Fragile X)
- Intellectual disability (known, or likely from history and examination)
- Head trauma with loss of consciousness for more than 5 minutes
- Significant neurologic disease, not counting TS (exceptions include febrile seizures or uncomplicated migraine)
- Severe or unstable systemic illness
- Factors (such as exaggerated signs) that in the judgment of the principal investigator make the video recording or YGTSS an inaccurate assessment of tic severity
- Judged by investigator to be unlikely to complete study procedures or to return for later visits
- Change in somatic or psychotherapeutic treatment in the 2 weeks preceding the first stimulation visit
- Planned change in somatic or psychotherapeutic treatment between the 2 stimulation visits

CONCOMITANT MEDICATIONS

Required: none

PROHIBITED MEDICATIONS

none

TREATMENTS AND DOSAGE

Rhythmic

- 10 Hz for 1-minute epochs (to replicate **Current Biology** report)

- 12 Hz for 5-minute epochs

Arrhythmic

- Same number of pulses per minute as in the rhythmic condition, but with a random inter-pulse interval, as implemented by the Nottingham group in the **Current Biology** report

Both

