Additional analysis details. Outliers will be determined at the level of the individual variables before the main analyses. If the distribution clearly deviates from a normal distribution on visual inspection because of outlying values, after transformation if appropriate, we will use a nonparametric analysis.

SAFETY MONITORING

We anticipate no adverse events other than possible mild, transient discomfort related to the stimulation. However, we will report any adverse events to the Institutional Review Board according to its regulations, including an annual summary.

No serious adverse events (SAEs) are expected. The PI will monitor for unanticipated problems, life-threatening events or deaths. If contrary to expectations any SAE occurs that the investigator considers possibly, probably or definitely related to participation in the study, we will confer with the IRB before continuing enrollment.

REFERENCES CITED

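### Minor: the CGI-I comparison is the one Aim 2 test that ignores visit; analysing it by randomised order would cost little and would protect power and precision if ratings shift between visits

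*Combined protocol and SAP*

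**What the plan says.** The trial is a two-session crossover, rhythmic on one day and arrhythmic on the other. The overview of participation states: "Session order is randomized and participants are blinded to order". It adds in parentheses: "Biological carryover effects are very unlikely". The allocation ratio and any blocking are not given.

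For Aim 2, the Data analysis section tests video-rated tic frequency and severity by a repeated measures ANOVA to "compare effects of visit, order (rhythmic day first or second) and stimulation" (on or off). It continues: "The hypothesized change is a significant interaction of visit, order and stimulation factors". The 1-minute blocks follow the same model: "A secondary analysis examines the last 40 s of the four 1-minute blocks in the same way".

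The next sentence deals with CGI-I, which is rated once per visit by the participant and once by the investigator (secondary outcomes 6 and 7): "Paired t tests will compare CGI-I ratings between stimulation conditions". No visit or order term is mentioned. Discomfort, blinding and interest in a portable device are only described, so CGI-I is the only Aim 2 comparison tested without visit.

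Under Additional analysis details, if outlying values make a distribution clearly non-normal then, "after transformation if appropriate, we will use a nonparametric analysis". That rule does not address visit.

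**The concern.** In a two-period crossover each person's rhythmic-minus-arrhythmic difference contains the visit effect, with its sign set by the order received. A paired t test pools the two orders and treats that systematic spread as noise. If ratings drift from visit 1 to visit 2 (for instance through familiarity or expectation, neither of which the documents quantify), the test loses power and the interval widens. If the completers' orders are also uneven, part of the drift enters the estimate for that sample. At stake is the precision of the only tested global ratings in Aim 2. The primary video outcomes are not affected.

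**Working it through.** **The plan's own figure.** The documents give no power or precision for CGI-I. The nearest figure is Aim 1: mean difference about 41, SD about 81, n = 32, two tails, 81% power. The standardised difference is 41/81 = 0.506. With alpha 0.05 (assumed), the noncentral t gives 79.2% and the normal approximation 81.7%, so the stated 81% is reproduced to within 2 points. I use a rounded 0.5 SD for CGI-I below. This is an assumption borrowed for scale.

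**Inputs**
- n = 32 completers (Sample size section).
- Assumed: true difference 0.5; SD of the within-person difference 1; normal continuous data; two-sided 5%; visit effect v (visit 2 minus visit 1) of 0, 0.25, 0.5 or 1.0 SD.
- Split of orders: not stated, so 16:16, 20:12 and simple randomisation are all shown.

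**Model.** Let d = rhythmic minus arrhythmic and τ the true difference.
- Rhythmic second (n1 people): mean of d is τ + v.
- Rhythmic first (n2 people): mean of d is τ − v.
- Paired estimate: τ + v(n1 − n2)/N.
- Paired variance at 16:16: 1 + v² × 32/31, so the SD grows by a factor of 1.03, 1.12 or 1.43 at v = 0.25, 0.5 or 1.0.
- With visit modelled, the estimate is the average of the two order means. Its standard error is ½√(1/n1 + 1/n2) with N − 2 degrees of freedom, and v cancels.

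**Orders 16:16** (simulation)

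| Visit effect (SD) | Paired t power | Visit modelled | Paired t type I error | Paired 95% interval width | Visit-modelled width |
|---|---|---|---|---|---|
| 0 | 78% | 78% | 5.0% | 0.72 | 0.72 |
| 0.25 | 76% | 78% | 4.3% | 0.74 | 0.72 |
| 0.5 | 70% | 78% | 2.9% | 0.80 | 0.72 |
| 1.0 | 48% | 78% | 0.5% | 1.02 | 0.72 |

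With no visit effect, the mean paired width is 0.740 at n = 30, 0.800 at n = 26 and 1.012 at n = 17. The widths of 0.74, 0.80 and 1.02 are therefore about those of 30, 26 and 17 participants.

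**Simple randomisation, averaged over splits**

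| Visit effect (SD) | Paired t power | Visit modelled |
|---|---|---|
| 0 | 78.2% | 76.7% |
| 0.10 | 77.8% | 76.8% |
| 0.15 | 77.4% | 76.9% |
| 0.25 | about 76% | about 77% |
| 0.5 | about 69% | about 77% |
| 1.0 | about 49% | about 77% |

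Mean bias is zero and paired type I error stays near 5%. The two methods break even at a visit effect of about 0.2 SD.

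**Given an uneven split.** At 20:12 with v = 0.5, the shift is 0.5 × (20 − 12)/32 = 0.125 SD, in either direction. Conditional type I error is 7.0%, against about 5% with visit modelled. A split at least this uneven has probability 0.215 under a Binomial(32, 0.5). Blocking would make it rarer but need not give 16:16 among completers, since "we will plan to enroll up to 44 participants to arrive at 32 who complete the entire study".

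**Cost of adjustment when there is no visit effect.** Besides one degree of freedom, variance is multiplied by N²/(4 n1 n2). At 16:16 this is 1, and power is 78.1% against 78.2%. At 20:12 it is 1024/960 = 1.067, and power is 75.5% against 78.2%.

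**The case against.** A paired t test is a standard and valid choice for a randomised crossover. The video outcomes need an ANOVA because stimulation on or off is a further factor. CGI-I is rated once per visit, so a simpler test contradicts nothing. CGI-I is secondary in a pilot that was not sized on it. Every magnitude here is assumed, the largest losses need a visit shift of a full SD, and the calculations use continuous data for a 7-point scale.

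All of this stands, and it fixes the weight of the point. Two stronger readings are tempting, and the documents do not support either.
- **That the CGI-I test is biased or has inflated error.** Order is randomised. Averaged over simple randomisation the estimate is unbiased with 5% type I error, and at 16:16 the test is conservative. A shift arises only conditional on an uneven realised split, and the documents report no split.
- **That any visit effect makes the paired test the worse choice.** Under simple randomisation it is no worse below about 0.2 SD, and the documents give no evidence for or against a visit effect on CGI-I.

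What remains is an asymmetry. Modelling visit loses about 1.5 points of power under simple randomisation if there is no visit effect. It gains about 1 point at 0.25 SD and 8 points at 0.5 SD.

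**Conclusion.** The point holds as a minor, inexpensive improvement. The plan uses visit and order for its other Aim 2 tests and gives no reason to leave them out for CGI-I. The possible loss is in power and precision, with a shift in the realised estimate only if completers' orders are uneven. Its size depends on a visit effect that the documents do not give: at 16:16 it is about 2 points of power at 0.25 SD, 8 at 0.5 SD and 30 at 1.0 SD. These figures rest on an assumed difference of 0.5 SD, 32 completers, a two-sided 5% level and normal data.

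**What to change.** In the Aim 2 text, replace the CGI-I paired t test, for each rater, with a model containing condition and visit, with participant as block. Report the rhythmic-minus-arrhythmic difference with its 95% interval.

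An equivalent route is to compare visit 2 minus visit 1 differences between the two order groups. The between-group difference is (τ + v) − (−τ + v) = 2τ. Half of it, and half its interval limits, must therefore be reported as the effect, with the sign set to rhythmic minus arrhythmic. This is the visit-by-order contrast already in the planned ANOVA, and it needs no assumption about carryover beyond the one the protocol already makes.

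If the nonparametric fallback applies, use a rank-sum test on the same visit differences and again halve any shift estimate.

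Record the change as a dated note to the registered plan before CGI-I data are joined to condition codes. The cost is one degree of freedom plus the variance inflation shown above when orders are uneven. Visits, timing and data collected do not change.
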